Appendix 2. Bristol Stool Chart

Bristol Stool Chart

Type 1		Separate hard lumps, like nuts (hard to pass)
Type 2		Sausage-shaped but lumpy
Type 3		Like a sausage but with cracks on its surface
Type 4		Like a sausage or snake, smooth and soft
Type 5		Soft blobs with clear-cut edges (passed easily)
Type 6		Fluffy pieces with ragged edges, a mushy stool
Type 7		Watery, no solid pieces. Entirely Liquid

Appendix 3. France Appendix

This appendix applies to study sites located in France.

1. GCP Training

Prior to enrollment of any subjects, the investigator and any subinvestigators will complete the Pfizer-provided Good Clinical Practice training course (“Pfizer GCP Training”) or training deemed equivalent by Pfizer. Any investigators who later join the study will complete the Pfizer GCP Training or equivalent before performing study-related duties. For studies of applicable duration, the investigator and subinvestigators will complete Pfizer GCP Training or equivalent every three years during the term of the study, or more often if there are significant changes to the ICH GCP guidelines or course materials.

2. Investigational Product

No subjects or third-party payers will be charged for investigational product.

1. VERSION HISTORY

This statistical analysis plan (SAP), Version 4, for Study B5091007 is based on the protocol administrative change letter (PACL) dated 02 Dec 2021.

Table 1. Summary of Major Changes in SAP Amendment

SAP Version	Change	Rationale
1	Not applicable	Not applicable
2	Amendment	Amendment to reflect protocol amendment 2
3	Amendment	Amendment to reflect protocol amendments 3 and 4, and revised analysis for missing data imputation
4	Amendment	Amendment to reflect the PACL dated 02 Dec 2021, which modified the plan to stop the study and perform the final analysis due to operational futility when at least 40 first primary Clostridium difficile infection cases in the per-protocol-3 population have accrued.

2. INTRODUCTION

This SAP provides the detailed methodology for summary and statistical analyses of the data collected in Study B5091007. A brief description of the study design and the study objectives are given. Subsequent sections include analysis populations and the definitions of the efficacy and safety endpoints followed by details around statistical analysis and reporting. A list of tables, listings, and figures, mock-up tables, listings, and figures, and programming rules are prepared separately based on the methods described in this document. This document may modify the plans outlined in the protocol; however, any major modifications of the primary endpoint definition or its analysis will also be reflected in a protocol amendment.

As of the PACL dated 02 Dec 2021, the study will be stopped and the final analysis will be performed due to operational futility when at least 40 first primary *Clostridium difficile* infection (CDI) cases in the per-protocol-3 (PP-3) population have accrued.

Three interim analyses were planned after 30, 40, and 50 first primary CDI cases, and only the first planned interim analysis was conducted. With this SAP amendment, while the statistical approach will remain the same, the final analysis will be conducted with all the available data at the study completion following the PACL.

2.1. Study Objectives

2.1.1. Primary Efficacy Objective

- To demonstrate that Pfizer's *Clostridium difficile* vaccine is effective in reducing the incidence of a first primary episode of CDI (case definition 1, [Section 3.4.1](#)).

2.1.2. Primary Safety Objective

- To evaluate the safety profile of Pfizer's *C difficile* vaccine as measured by the percentage of subjects reporting local reactions and systemic events, adverse events (AEs), and serious adverse events (SAEs).

2.1.3. Secondary Efficacy Objectives

Secondary efficacy objectives of Pfizer's *C difficile* vaccine will be evaluated for the 3-dose family and the 2-dose family after primary objectives are met. The objectives included as secondary, and the order in which they will be analyzed, were determined on the basis of their potential public health importance and their potential to be adequately powered. The objectives within each family will be evaluated sequentially in the following order:

- For the 3-dose family:
 1. To evaluate the efficacy of Pfizer's *C difficile* vaccine in reducing:
 - The incidence of all CDI cases (see case definitions 1 and 2, [Section 3.4.1](#) and [Section 3.4.2](#)).
 2. To evaluate the efficacy of Pfizer's *C difficile* vaccine in reducing the severity of CDI, defined by:
 - The duration of CDI episodes.
 - The requirement to seek medical attention.
 3. To evaluate the efficacy of Pfizer's *C difficile* vaccine in reducing the incidence of recurrent CDI (see case definition 2, [Section 3.4.2](#)).
- For the 2-dose family (at-least-2-dose/only-2-dose family).
 - In subjects who received at least 2 doses of vaccine.
 1. To evaluate the efficacy of Pfizer's *C difficile* vaccine in reducing:
 - The incidence of all CDI cases (see case definitions 1 and 2, [Section 3.4.1](#) and [Section 3.4.2](#)).
 2. To evaluate the efficacy of Pfizer's *C difficile* vaccine in reducing the incidence of recurrent CDI (see case definition 2, [Section 3.4.2](#)).
 - In subjects who received only 2 doses of vaccine.
 3. To evaluate the efficacy of Pfizer's *C difficile* vaccine in reducing:

Subjects will be randomly assigned in parallel in a 1:1 ratio to receive *C difficile* vaccine (200 µg total toxoid) or placebo (saline).

This is an event-driven study with a total target of 66 first primary CDI cases (meeting case definition 1 in the PP-3 population, [Section 3.4.1](#) and [Section 4.2](#)) to be accrued for the study; the total enrollment number may vary depending on the incidence rate of the primary endpoint, true underlying vaccine efficacy (VE), and potential early stop for efficacy or futility.

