9.1. Sample Size Determination

This study is placebo-controlled, event-driven, and randomized with a 1:1 randomization ratio between subjects receiving *C difficile* vaccine and placebo.

With assumptions of a true adjusted VE of 66.5% after 3 doses of investigational product, 66 first primary CDI cases (meeting case definition 1 in the per-protocol-3 population [Section 2.1.1](#) and [Section 9.2.1](#)) will provide 89.8% power to conclude true VE of >20%, taking into consideration 3 interim analyses ([Section 9.5](#)) during the study.

The early efficacy stopping boundaries are based on a GS design⁶⁵ utilizing a single-binomial distribution, conditional on a total of 66 cases, assuming true VE of 66.5%, with 3 interim analyses at 30, 40 and 50 cases.⁶⁵ The same gamma[-2] alpha spending function that was used for the original statistical design is also used for this modified statistical design.

As this is an event-driven and GS study, the total enrollment number may vary depending on the assumptions of incidence rate of the primary endpoint, true VE, and potential early stop for efficacy or futility.

Update as Part of Amendment 2 (January 2019):

Based on the ongoing blinded review of pooled primary CDI events, the annual CDI incidence rate in the placebo group may be different from the assumed rate in the power calculation during the initial study design. Additional enrollment may be needed in order to maintain the study power of 90% (106 first primary CDI cases in the final analysis) to reject the null hypothesis of $VE \leq 20\%$. Assuming a true VE of 60% after 3 doses of investigational product and the true annual CDI rate in the placebo group of 0.552% to 0.516%, which is 8 to 14% lower than the previously assumed 0.6%, an additional 1369 to 2566 subjects may be needed to ensure the required number of first primary CDI cases.

In light of this, it is planned to enroll approximately 1700 additional subjects, giving a total of approximately 17,476 subjects. The pooled primary CDI event rate for the total population will continue to be monitored by the study team in a blinded manner and a further adjustment to enrollment may be required.

Update as Part of Amendment 4 (July 2020):

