9.2.1. Analysis of the Primary Endpoints

VE is defined as $VE = 100 \times (1 - IRR)$, where IRR is the infection rate ratio, the calculated ratio of first primary CDI incidence between the *C difficile* vaccine group and the placebo group. VE_i will be evaluated separately after 3 and after 2 doses. The 2 primary efficacy hypotheses are (in order of fixed-sequence testing):

1. $H_{03}: VE_3 \leq 20\%$ vs $H_{a3}: VE_3 > 20\%$, and
2. $H_{02}: VE_2 \leq 20\%$ vs $H_{a2}: VE_2 > 20\%$.

where H_{0i} and H_{ai} represent null hypothesis and alternative hypothesis, and VE_i ($i = 2, 3$) represents VE after at least 2 doses and after all 3 doses, respectively. For subjects with multiple primary CDI cases, only the first primary case will contribute to the VE calculation in each hypothesis test.

The primary efficacy hypotheses will be tested by a 1-sided test for $VE > 20\%$ by a fixed-sequence testing procedure, with testing order of H_{03} followed by H_{02} using the approach described in Chan and Bohidar,⁶³ accounting for follow-up time after vaccination. Statistical inference will be based on the lower alpha-adjusted confidence interval (CI) for VE_3 , and VE_2 .

If the study continues after all 3 of the interim analyses, once 66 first primary cases after 3 doses have accumulated for the final analysis, the hypothesis test H_{03} will be performed first, and the null hypothesis H_{03} will be rejected if there are 20 or fewer cases observed in the *C difficile* vaccine group (corresponding to a 2-sided lower bound of 96.4% exact CI $> 20\%$), assuming equal follow-up times. The lower bound of the 2-sided 96.4% exact CI corresponds to $\alpha = 0.018$ (one-sided) used for final testing in a GS design with a gamma(-2) efficacy boundary. Only if the hypothesis H_{03} is rejected, then hypothesis testing for H_{02} will be performed, at the same significance level for VE_2 for the final analysis. The statistical success criterion for H_{02} also corresponds to the lower bound of the 2-sided 96.4% CI for VE being $> 20\%$. If there is failure to reject the hypothesis H_{03} , the hypothesis test H_{02} will not be performed.

The statistical analysis specifications for the primary endpoints are summarized in Table 6.

Table 6. Statistical Analysis Specifications for the Primary Endpoints

Primary Endpoints	Time Period for Case Accrual	CDI Case Definition	Analysis Population	Hypothesis Testing ^a	Statistical Testing Method

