2.2.2. Number of Subjects

It is anticipated that approximately 17,476 adults, 50 years of age and above, will be enrolled globally to accumulate 66 first primary CDI cases (meeting case definition 1, [Section 3.4.1](#)). As this is an event-driven and group-sequential (GS) study, the final enrollment number may vary depending on the incidence rate of the primary endpoint, true underlying VE, and potential to stop early for efficacy or futility. The number of subjects enrolled in each country and at each site will vary based on enrollment capabilities.

To achieve a broad representation of age groups among those 50 years of age and older, and achieve an adequate rate of CDI, the numbers of subjects intended to be enrolled in each of 4 age groups are shown in Table 2.

Table 2. Intended Number of Subjects Included in the Study, by Age Group

Category	Subcategory	Minimum Number for Inclusion	Maximum Number for Inclusion
Age	50-59 years	800 subjects	1600 subjects
	60-69 years	1600 subjects	Not limited
	70-79 years	1600 subjects	Not limited
	≥80 years	400 subjects	Not limited

On monitoring the pooled primary CDI event rates in different age groups, inclusion criteria subgroups, Charlson Comorbidity Index (CCI) subgroups, and subgroups based on other baseline factors ([Table 3](#)), once the specified minimum numbers in each age group have been achieved, if a substantially higher pooled CDI event rate is observed in some subgroups, the intention may be to stop enrollment in lower-risk subgroups and complete enrollment with the higher-risk subgroups thereafter. This is mainly to help to achieve the targeted total number of first primary cases in a timely manner.

Table 3. Number of Subjects in Other Categories to Be Monitored for Inclusion in the Study

Category	Subcategory
Charlson Comorbidity Index	0
	1
	2
	3
	≥4
Subject inclusion criterion 4	At least 1 inpatient hospitalization ≥2 nights' duration in the previous 12 months.
	At least 2 emergency room visits in the previous 12 months.
	At least 10 outpatient visits (primary and/or secondary care visits but excluding pharmacy and mental health visits) in the previous 12 months.
	Residence in a skilled nursing facility (a residential institution that provides professional nursing care and rehabilitation services, usually following discharge from the hospital).
	Residence in a nursing home (a residential institution that provides assistance with activities of daily living).

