Study futility at each interim analysis will be evaluated based on the preidentified case split (*C difficile* vaccine vs placebo) by analysis of conditional power (CP). The conditional probability of study success at the final analysis with observed VE of at least 59.6% (19 out of 66 cases) is calculated based on assumed case split in the *C difficile* vaccine group and the adjusted true VE of 66.5% remains for the rest of the study. The case split for futility is 11 vs 19 for IA1 (corresponding to a CP cutoff of 50%), 13 vs 27 for IA2 (corresponding to a CP cutoff of 60% at 40 cases), and 16 vs 34 for IA3 (corresponding to a CP cutoff of 60% at 50 cases). These futility boundaries may be subject to change to reflect subsequent program-related decisions by the sponsor.

Incorporation of the planned interim analyses is a source of multiplicity and its effect on the overall type I error for the study is accounted for in the CI adjustments for H_{03} at the interim analyses and at the final analysis. These values were chosen to be consistent with the statistical design operating characteristics put forth in the protocol, which utilized a GS design with 3 interim analyses at 30, 40, and 50 first primary CDI cases, respectively, and a gamma (-2) alpha spending function. The protocol provides an example of the statistical design operating characteristics under particular anticipated counts of total cases at the interim analyses and final analysis.

As of the PACL dated 02 Dec 2021, the first interim analysis with 30 cases of first primary CDI was conducted as planned in protocol amendment 4. The recommendation from the external data monitoring committee (E-DMC) was to continue the study because the criteria to stop for efficacy or futility were not met. Due to operational futility of slow case accrual and increased subject withdrawals, the study will be stopped and a final analysis will be performed with all available data at the completion of the study following the PACL.

For the final analysis of the first primary endpoint, the VE CI with an alpha level of 0.018 (1-sided), which was planned for the final analysis, will be used in the VE evaluation (Section 5.1.1). Since only 1 interim analysis (with 1-sided alpha level of 0.006) was conducted, the overall type I error for this primary efficacy endpoint is still controlled at the 0.025 level.

CCI [REDACTED]

CCI [REDACTED]

[REDACTED]

CCI [REDACTED]

[REDACTED]

CCI [REDACTED]

[REDACTED]

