7.2. Interim Analyses and Summaries

Prior to the PACL dated 02 Dec 2021, the following interim analyses and summaries were planned. At each interim analysis, the primary efficacy endpoint of H_{03} : $VE \leq 20\%$ vs H_{a3} : $VE > 20\%$ will be evaluated on the PP-3 population. The total number of cases reported, the number of subjects available in the population, the number of 1000 person-years, and the infection rate by vaccine group will be descriptively presented. The VE point estimate and the corresponding 2-sided 98.8% CI for interim analyses 1 and 2 and 98.2% CI for interim analysis 3 (adjusting for multiplicity as discussed in [Section 5.1.4](#)) will be calculated.

Hypothesis tests for H_{02} may be performed on the PP populations in a hierarchical fashion as described in [Section 5.1.2](#) and will only be performed outside the context of the interim analysis meeting (ie, only information pertaining to H_{03} will be reviewed at interim analysis and serve as the basis for the decision to stop or to continue the trial).

The probabilities of stopping the trial for success are 44.3% at interim analysis 1 (ie, observe ≤ 6 cases in the *C difficile* vaccine group), 15.0% at interim analysis 2 (ie, observe ≤ 9 cases in the *C difficile* vaccine group), and 17.1% at interim analysis 3 (ie, observe ≤ 13 cases in the *C difficile* vaccine group) if the true VE is 70%.

Furthermore, safety data including reactogenicity, AEs, and SAEs reported will be summarized similarly as for the CSR and described in [Section 6](#) of the SAP. Reporting will occur at defined time points outlined in the E-DMC charter as well as for the interim analysis.

Blinded summaries will be provided to the study team and unblinded summaries will be provided and presented to the E-DMC members at scheduled E-DMC meetings.

At each interim analysis, the conditional power of the study to reject the original null hypothesis, conditional upon the results accumulated so far, will be calculated. Futility may be declared and the study may cease enrollment, if the conditional power falls below the prespecified cutoff value. This futility analysis will be applied to the primary endpoint only, in the PP-3 efficacy population. [Table 27](#) describes the statistical design operating characteristic modeling based on the modified study design.

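### SAP v4 ends the trial at 40 or more PP-3 cases but still gives 66 as the current target, and the only stated H03 power at the design VE (89.8%) belongs to the 66-case design

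*SAP*

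**What the plan says.** **The stop.** SAP section 2 says that "the study will be stopped and the final analysis will be performed due to operational futility when at least 40 first primary" CDI cases in the PP-3 population have accrued. Table 1 in section 1 says the same. Section 5.1.2 adds that only the first interim analysis was done, that "the criteria to stop for efficacy or futility were not met", and that all available data will be used at the end.

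**The level.** SAP 5.1.2 keeps the planned level for H03: "the VE CI with an alpha level of 0.018 (1-sided), which was planned for the final analysis, will be used in the VE evaluation". Success is a lower limit of the 96.4% exact CI above 20% (SAP 5.1.1 and Table 16).

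**The target.** The study-design description (SAP 2.2.1) reads "This is an event-driven study with a total target of 66 first primary CDI cases". SAP 2.2.2 says that about 17,476 adults "will be enrolled globally to accumulate 66 first primary CDI cases". Section 2.2.2 carries no note that this is superseded. The same holds for 2.2.1 as far as it can be read, but its heading and opening lines are missing from the extracted text. Elsewhere the SAP does mark older text: 7.2 opens with "Prior to the PACL dated 02 Dec 2021, the following interim analyses and summaries were planned", and 5.1.2 and 7.1 have similar notes.

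**The power.** Protocol 9.1 says that, at a true adjusted VE of 66.5%, 66 cases "will provide 89.8% power to conclude true VE of >20%, taking into consideration 3 interim analyses". Protocol 9.2.1 says that, at 66 cases, H03 "will be rejected if there are 20 or fewer cases observed in the" vaccine group. The visible text gives no power for a final analysis at 40 or more cases.

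**The concern.** The SAP carries a study size that the study will not reach, and the power quoted for the primary hypothesis rests on that size. A final analysis at 40 to 50 cases after one interim look has different operating characteristics.

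What is at stake is how a non-significant result is read. Someone who takes 89.8% as the power would treat failure to reject H03 as fairly strong evidence that VE falls short of 66.5%. At exactly 40 cases, H03 would fail about 41% of the time even if VE were 66.5%. H03 also gates H02, and the secondary families are tested only after the primary objectives are met, so the lower power carries through the whole confirmatory sequence.

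**Working it through.** **Inputs.** Null VE 20% and design VE 66.5% (protocol 9.1). IA1 efficacy boundary: 6 or fewer of 30. Later efficacy boundaries in the 66-case design: 9 of 40, 13 of 50, 20 of 66. Futility: 11 or more, 13 or more, 16 or more at the three interims (protocol 9.5). Final one-sided level 0.018 (SAP 5.1.2). Equal person-time is assumed, as in the note to SAP Table 27.

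**Model.** Given n cases, vaccine cases are Binomial(n, p) with p = (1 − VE)/(2 − VE).
- Null: p0 = 0.8/1.8 = 0.4444.
- Design: p1 = 0.335/1.335 = 0.2509.

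**Step 1: reproduce the plan's figures.**
- Normal approximation with gamma(−2) spending at 30, 40, 50 and 66 cases (null variance in the test, alternative variance for power): nominal levels 0.0058, 0.0061, 0.0089 and 0.0182, matching 0.006, 0.006, 0.009 and 0.018. Power is 89.6%, against the stated 89.8%.
- Exact calculation over the case boundaries with futility applied, at VE 70%: 0.8479, as in Table 27.
- The same exact calculation at VE 66.5%: 87.6% with futility not applied, 75.5% with it applied.

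So 89.8% is a normal-approximation figure. The exact comparator for what follows is 87.6%, or 75.5% with futility.

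**Step 2: final cutoff.** The cutoff c is the largest count with P(Bin(n, p0) ≤ c) ≤ 0.018, which is equivalent to the 96.4% Clopper-Pearson rule. At n = 40, P(≤10) = 0.0090 and P(≤11) = 0.0212, so c = 10. The observed VE at the cutoff is 1 − 10/30 = 66.7%. At 66 cases it is 1 − 20/46 = 56.5%.

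**Step 3: power of the revised design.** With X the vaccine cases among the first 30:

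Power = P(X ≤ 6) + Σ P(X = k) · P(Bin(n − 30, p1) ≤ c − k)

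The sum runs over k = 7 to c with futility not applied, and over k = 7 to 10 with IA1 futility applied. At VE 66.5%, P(X ≤ 6) = 0.3437 and P(7 ≤ X ≤ 10) = 0.5483.

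| Final cases | c | Observed VE at c | Power, no futility | Power, futility applied |
|---|---|---|---|---|
| 40 | 10 | 66.7% | 59.2% | 59.2% |
| 41 | 11 | 63.3% | 68.3% | 68.1% |
| 43 | 11 | 65.6% | 62.4% | 62.2% |
| 45 | 12 | 63.6% | 68.0% | 67.5% |
| 49 | 14 | 60.0% | 77.5% | 75.7% |
| 50 | 14 | 61.1% | 75.1% | 73.5% |
| 55 | 16 | 59.0% | 80.7% | 77.9% |
| 66, four looks | 20 | 56.5% | 87.6% | 75.5% |

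Power does not rise steadily with the count because the cutoff is a whole number. The normal approximation gives 66.7% at 40 and 77.9% at 50, against 89.6% at 66.

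**Step 4: given that IA1 crossed neither boundary.** If the stated boundaries were used, X was 7 to 10. The chance of success is then (power with futility − 0.3437)/0.5483. At 40 cases this is (0.5922 − 0.3437)/0.5483 = 45%; at 45 it is 60% and at 50 it is 71%. Had the 66-case plan continued from the same point, it would be 88% with later futility not applied, or 75% with it applied.

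**Step 5: type I error.** The Step 3 formula at p0 gives 0.0109 at 40 cases and 0.0151 at 50. Over 40 to 50 the range is 0.0107 (at 46) to 0.0189 (at 49), all below 0.025.

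**Step 6: sensitivity.** With a person-time ratio of 0.95 to 1.05 and cutoffs recomputed, exact power over 40 to 50 cases (futility not applied) ranges from 57% to 79%.

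**The case against.** The best reply is that nothing is hidden and nothing is undefined. Several parts of it stand.

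- **The stop is disclosed.** Sections 1 and 2 state it, and 5.1.2, 6.1.1 and 7.1 repeat that the final analysis will go ahead. A reader might infer that the SAP conceals the change or that analysts would wait for 66 cases. The text does not support that. The leftover target is an inconsistency to reconcile.
- **Success is fully defined.** A reader might infer that the decision rule is missing because the only final cutoffs refer to 66 cases. It is not missing. The 96.4% exact CI rule works at any count, and SAP 5.2.2.2 gives formulas that include person-time. The documents also use 19 of 66 (observed VE 59.6%) as final success in the conditional-power text, so 20 of 66 is not the only final figure in print.
- **Relevant text may exist out of sight.** SAP 5.1.3 (underrunning and overrunning case counts) is redacted, as is text directly after the 0.018 paragraph in 5.1.2. The change letter is not among the documents. So it cannot be said that the plan lacks a revised power, only that the visible text does not give one.
- **The size depends on convention.** Setting 59% against 87.6% pairs the lowest possible count with a comparator that ignores futility. With futility applied, the 66-case design itself has 75.5%, and the gap at 50 cases is about 2 points, partly because two futility looks have been dropped.

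It is also argued that power no longer matters once a trial stops for slow accrual, since the CI shows the precision. The CI does show it. But a power figure remains on record, and stating what it applies to before unblinding is more credible than explaining it afterwards.

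**Conclusion.** The point holds as a reconciliation and reporting matter. SAP 2.2.2, and 2.2.1 as far as it is visible, should not give 66 cases as the current target, and 89.8% does not describe the analysis that will be run.

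The size rests on VE 66.5%, equal person-time and exact calculation. With futility not applied, power falls from 87.6% to 59% at the 40-case floor, 62% to 78% over 41 to 50 and 81% at 55. With futility applied, the fall is from 75.5% to 59% at 40 and to 74% at 50. The counts above 40 are assumptions, because the SAP says only that there will be at least 40.

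A reader might also infer that keeping 0.018 after an unplanned change inflates type I error. It does not: the overall error is 0.011 to 0.019 over 40 to 50 cases. The statement of more than 90% power for H02 is conditional on success for H03 and is not in question here.

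**What to change.** 1. In SAP 2.2.1 and 2.2.2, mark the 66-case target as the plan before the change letter of 02 Dec 2021 and state the stop at 40 or more PP-3 cases.
2. Before unblinding, state (naturally in 5.1.2, after the 0.018 sentence) that 89.8% applies only to the 66-case design, and give power for a few plausible final counts. Name the VE, the method (exact or normal), the futility convention and the person-time assumption.
3. If section 5.1.3 or the change letter already gives these figures, cross-refer to it from 2.2.1, 2.2.2 and 5.1.2 instead.

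A table of case cutoffs is optional. If added, it should be labelled illustrative, since the CI rule with actual person-time decides.

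The cost is a short text edit and one small table. The test, level, endpoint, population and data stay as they are, so the condition in SAP section 2 for a protocol amendment is not met.
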